### **3.1 General Design**

Participants will be randomized into one of two study groups. Both groups will receive standard buprenorphine maintenance treatment. Participants will attend study visits twice weekly for 12 weeks and a close-out visit in week 13. One group will be assigned to Remote Observed Dosing (ROD) and will have all of their Suboxone® doses remotely observed using procedures described below. The attention control (AC) group will not have their dosing observed but will send a text message confirming they have taken their study medication to the study team daily matching contact with the study team.

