video Skype call with study staff. Data from that study reveal low rates of continued opioid use while on Suboxone® and high rates of Skype-observed doses. All urines tested during the study were buprenorphine positive, demonstrating excellent adherence with the treatment. In addition, self-reports of opiate use corresponded to urine drug screen results, and only one participant continued to test positive for opioids intermittently during the study. ***Participants successfully completed 100% of required in-office visits, and 90% of scheduled Skype calls. Perhaps more important, participants did not find the daily Skype calls to be burdensome.***

However, the pilot study did not have a control group and because the clinic was only open Monday-Friday, we did not observe dosing on the weekends. While this is true for many physician offices and community based treatment providers, it is problematic because weekends are often a high risk time for drug users. It is important to observe dosing 7 days a week in order to ensure optimum adherence and avoid diversion. It is equally important to determine if ROD improves buprenorphine adherence compared to an attention-matched control group.

[name] has developed a protocol that uses a ***smartphone to video record buprenorphine dosing and automatically sends this recording through HIPAA compliant means to clinical staff who can then review it at a convenient time and location.*** Her protocol also uses SMS text messaging to communicate with patients. To address the feasibility of patients with an OUD using this technology, [name] conducted a pilot study with 71 patients in OUD treatment locally regarding the feasibility and usability of such a technology. The preliminary data indicated:

- While 95% of patients had a cell phone, the majority of them (76%) had “pay as you go” plans with limited data capabilities. In addition, 71% reported changing their cell phone regularly.
- 87% reported sending and receiving SMS text messages daily, 60% used the video option on their phones to send videos, 54% watched videos online, and 53% used an “instant message app”.
- 78% reported they would take part in a text messaging program to help prevent relapse and 75% reported they would be receptive to a cell-phone based OUD intervention.

***These findings suggest using the proposed platform to monitor buprenorphine dosing is both feasible and would be welcomed by patients undergoing opioid treatment.***

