## **3 Investigational Plan**

Forty patients with OUD, who are not currently prescribed buprenorphine, will be recruited through the University of Pennsylvania's Center for the Studies of Addiction (CSA), an outpatient substance abuse treatment facility. Potential participants will be screened for physical and psychological appropriateness for inclusion in the study using the CSA standard intake procedures. This includes a psychosocial diagnostic evaluation, a medical exam, urine and blood tests, and an EKG (see Measures for full description of screening assessments). Participants who are appropriate for the trial will be inducted onto Suboxone® using standard office based induction as described in the ASAM National Practice Guideline for the Use of Medications in the Treatment of Addiction Involving Opioid Use (Kampman and Jarvis 2015).

All patients will receive buprenorphine (Suboxone®; up to 24 mg daily) and will be randomly assigned to one of two groups. The experimental group (n=20) will receive daily remote observed dosing (ROD) via a secured video platform that records dosing using study-provided smartphones (approximately 5 minutes each session). ROD videos will be monitored daily for compliance. The attention control group (AC, n=20) dosing will not be observed. All subjects will attend 2 weekly study visits (3 study visits during the induction phase in Week 2). Study visits starting in Week 3, after the Induction phase, will consist of counseling in the form of weekly Medication Management (MM); buprenorphine distribution with medication management; and a urine screen. Study visit 4 will consist of a urine screen and phone management task (downloading study related videos) for those randomized to the Remote Observed Dosing Group.

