Hamilton Depression Rating Scale (Hamilton 1967). The Ham-D is a 20-minute, 24-item interview that measures the severity of depression and changes in depressive symptoms. The Ham-D is administered at baseline, week 9 and at the end of the study.

Locator Form. The locator form asks about addresses and phone numbers where the participant might be contacted, as well as names and addresses of other individuals who might know the participant's whereabouts. The information is used to locate participants who do not respond to a calls and weekly text messages.

Obsessive Compulsive Drug Use Scale (Franken, Hendriks, and van den Brink 2002). Adapted from the Obsessive Compulsive Drinking Scale(Anton, Moak, and Latham 1995) (OCDS), measures craving for heroin on a 12-item likert scale. Our version replaces heroin with opioids more generally. This will be administered at baseline and weekly throughout the trial.

Risk Assessment Battery (Metzger et al. 1993). The RAB is a 38 item self-report questionnaire which assesses high risk behavior for exposure to the HIV virus. The RAB yields drug, sex and total risk scores and will be administered at baseline and at the end of the trial.

Systems Usability Scale (Grindrod, Li, and Gates 2014). The SUS is a 10 item self-reported validated measure of learnability and user satisfaction that we will use to evaluate the remote medication monitoring protocol. It uses a 5-point Likert scale to provide a quantitative measure of the usability of the ROD protocol and provides an overall score between 0 and 100. This scale will be administered at the end of the study.

Timeline Follow Back Interview (Sobell and Sobell 1995). The TLFB is a 15-30 minute, semi-structured interview adapted by our laboratory to collect information about daily drug, alcohol, and nicotine use. The TLFB will be given by trained research staff at baseline to cover 3 months immediately preceding treatment entry and will be updated at each research visit to determine any time spent in a controlled environment and cocaine, nicotine, and other drug use during the

CONFIDENTIAL

period since the last visit. The composite of these assessments are additive over the course of the study so that we will have continuous data.

Video Compliance. Submission of videos will be recorded (date and time) and assessed daily for compliance (i.e., taking the medication as prescribed). In addition, videos will be saved off the micro-SD cards at each office visit.

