### **Secondary Study Endpoints**

We will use a combination of self-report and (nor)buprenorphine levels to classify patients in the AC group as adherent or non-adherent for each study day to compare their rates of adherence to the (video-verified) rates in the ROD group. These comparisons will give a direct estimate of the improvement in adherence likely to be observed between the proposed method and standard methods.

Rates of illicit opiate use will be compared between the groups using combinations of urine drug screens (UDS) and TLFB self-reports obtained at each visit.

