## **6.2 Statistical Methods**

For the ROD group, we will calculate the within-patient proportion of study days on which video captured adherence, as per protocol. We will use these data to compare observed adherence rates in this group to rates reported in prior studies. The primary comparison between the groups will use the creatinine normalized weekly quantitative urine levels for buprenorphine and norbuprenorphine. Exploratory analyses include the following: We will use a combination of self-report and (nor)buprenorphine levels to classify patients in the AC group as adherent or non-adherent for each study day, and use mixed effects logistic regression models to compare their rates of adherence to the (video-verified) rates in the ROD group. Rates of illicit opiate use will be compared between the groups using combinations of urine drug screens(UDS) and TLFB self-reports obtained at each visit. The ASI, CGI, and HAM-D scales are obtained monthly. To assess usability and acceptability of the ROD protocol and text messaging application, [name] will conduct semi-structured interviews and analyze data from the Systems Usability Scale (SUS) at the final office visit.

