## 13 Appendices

**Table 1: Assessment Schedule**

| Assessment  | Baseline
(V1) | Week
2 (V2-
V4) | Weeks 3-14
(V5-V28) | End of
Study
(V29) |
|---|------------------|-----------------------|------------------------|--------------------------|
| Medical Exam and EKG, CBC and blood chemistry, Urinalysis (UA), Risk Assessment Battery           | 1X               |                       |                        | 1X                       |
| Pregnancy Test (women), Addiction Severity Index (ASI)  | 1X               |                       | 2X, weeks 5 and 9      | 1X                       |
| Urine Toxicology and Urine Buprenorphine and Norbuprenorphine Screen, Timeline Follow back (TLFB) | 1X               |                       | 24X                    | 1X                       |
| Clinical Global Impression Scale (CGI), Hamilton Depression Rating Scale (HAM-D)                  | 1X               |                       | 1X, week 9             | 1X                       |
| Columbia Suicide Severity Rating Scale (C-SSRS), Obsessive Compulsive Drug Use Scale (OCDUS)      | 1X               |                       | 12X                    |                          |
| Systems Usability Scale (SUS)   |                  |                       |                        | 1X                       |
| Concomitant Medications   | 1X               | 3X                    | 24X                    | 1X                       |
| Medical Management, Pill Distribution   |                  | 3X                    | 12X                    |                          |
| Adverse Events  |                  | 3X                    | 24X                    | 1X                       |
| Video Compliance/Attention Control (7 days per week, weeks 3-14)                                  |                  |                       | 84X                    |                          |

CONFIDENTIAL

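### As described, the control arm's daily self-report can confirm a dose but not record a missed one, so day-by-day classification cannot separate a missed dose from an untexted one

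*Combined protocol and SAP*

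**What the plan says.** Section 3 states that "The attention control group (AC, n=20) dosing will not be observed". Section 3.1 gives this arm a daily contact to match attention: participants "will send a text message confirming they have taken their study medication to the study team daily". Table 1 schedules it as "Video Compliance/Attention Control (7 days per week, weeks 3-14"), 84 times, beside 24 urine collections in the same weeks.

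The Secondary Study Endpoints in 3.4 then say: "We will use a combination of self-report and (nor)buprenorphine levels to classify patients in the AC group as adherent or non-adherent for each study day". Section 5.6 repeats this. Section 6.2 adds that the analysis will "use mixed effects logistic regression models to compare their rates of adherence to the (video-verified) rates in the ROD group".

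The other places where a missed dose might be recorded are these:
- **TLFB (3.3):** described as "adapted by our laboratory to collect information about daily drug, alcohol, and nicotine use". The update at each visit names time in a controlled environment and cocaine, nicotine and other drug use. Study medication is not named.
- **Visit questions (5.2.3):** other medications, drug and alcohol use, and side effects.
- **Medication Management (section 5):** a weekly contact that touches on compliance. Section 3.3 lists no dose record from it.
- **Table 1:** lists pill distribution but no pill count.

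The plan does not say which self-report is meant, how a day without a text is coded, or how a urine level is assigned to particular days.

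**The concern.** The task in 3.4 is to "classify patients in the AC group as adherent or non-adherent for each study day". That needs information that can come out either way on each day. A text that confirms dosing supplies only one of the two answers. Its absence may mean a missed dose or a dose taken without a text, and nothing else described in the plan separates the two on a day without urine.

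The analyst must therefore pick a rule after the fact: missed, taken or missing. The three rules give different control-arm rates, so the contrast with ROD partly reflects the rule and the participants' texting habits. The plan presents this contrast as directly estimating the gain in adherence, and section 2.1 includes it in the primary objective. Daily reports that were never collected cannot be recovered at analysis.

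**Working it through.** **The plan's own counts.** Days to classify per AC participant: 12 weeks × 7 = 84. Urines in the same weeks: 12 × 2 = 24. Both agree with Table 1.

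**Days without a same-day sample.** 84 − 24 = 60, and 60/84 = 71.4%. With 20 AC participants and no dropout, that is 20 × 60 = 1,200 of 20 × 84 = 1,680 person-days. This is the share of days on which a missing text could not be checked against urine from that day. It is not the number of days without a text, because the documents give no texting rate.

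**Effect of the coding rule.** Let a be true adherence and t the share of taken doses that are texted. Assume that urine resolves each of the 24 sampled days correctly and that no text is sent for a missed dose. These are assumptions for illustration. The scored adherence is:
- untexted counted as missed: (24a + 60at)/84
- untexted days without urine dropped: (24a + 60at)/(24 + 60at)
- untexted counted as taken: (24a + 60)/84

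For a = 0.80, t = 0.90: (19.2 + 43.2)/84 = 74%; 62.4/67.2 = 93%; 79.2/84 = 94%.

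For a = 0.50, t = 0.90: (12 + 27)/84 = 46%; 39/51 = 76%; 72/84 = 86%.

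| True adherence | Texted if taken | Untexted = missed | Dropped | Untexted = taken |
|---|---|---|---|---|
| 80% | 100% | 80% | 93% | 94% |
| 80% | 90% | 74% | 93% | 94% |
| 80% | 80% | 69% | 92% | 94% |
| 80% | 70% | 63% | 92% | 94% |
| 50% | 100% | 50% | 78% | 86% |
| 50% | 90% | 46% | 76% | 86% |
| 50% | 80% | 43% | 75% | 86% |
| 50% | 70% | 39% | 73% | 86% |

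No rule is right throughout. Counting untexted days as missed is exact only if every taken dose is texted.

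**If a sample also informs earlier days.** The documents give no detection window. Assuming visits 3 and 4 days apart, the days left uncovered (u) are 37 (44%) for a 2-day window, 14 (17%) for 3 days and 3 (4%) for 4 days. The gap between the missed and taken rules is u(1 − at)/84. With t = 0.90:

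| u | Gap at a = 0.80 | Gap at a = 0.50 |
|---|---|---|
| 60 | 20 points | 39 points |
| 37 | 12 points | 24 points |
| 14 | 5 points | 9 points |
| 3 | 1 point | 2 points |

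The smaller gaps hold only if a level reveals the status of each day in its window. A level that spans several days does not by itself show which day was missed, and the plan gives no rule for assigning it.

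**The case against.** The strongest reply is that the plan is silent rather than wrong. No text template or TLFB form is shown, section 1.1 describes text messaging used to communicate with patients, and the TLFB's other drug use is open-ended. A reply for a missed dose, or a TLFB question on study medication, is not excluded. That stands, and it is why the point is limited to what is described. The protocol still has to name its self-report source.

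Second, the urines are quantitative parent and metabolite levels, to be read with a toxicology consultant. A reader might infer that at least 60 days rest on self-report alone. The documents do not support that: with full attendance, 60 is the most that could lack urine information. It is a minimum only if one sample informs one day.

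Third, a reader might infer that the problem favours ROD. It need not. The endpoint in 3.4.1 counts only days on which video captured adherence, so an unrecorded ROD dose also scores against the participant. Coding untexted AC days as missed treats a failed contact alike in both arms. False confirming texts would push AC adherence upward.

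Fourth, two sources of a texting-failure rate are tempting, and neither serves. The pilot's missed calls were weekday video calls with staff, not texts that participants send themselves. Its positive urines do not show that doses were taken on missed-call days. The phone-use survey does not translate into lost AC days either: section 3 ties study phones to ROD, but 5.2.2 lists smartphone distribution without naming an arm, and no length of gap is given.

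Finally, 6.2 calls this comparison exploratory, and the primary between-group model in 6.3.2 uses urine levels only. That limits how serious the point is.

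**Conclusion.** The point holds in limited form. As described, the AC arm's only daily report of study medication is a confirmation. The plan requires a yes-or-no status for each of 84 days, 60 of them (71%) without same-day urine, and has no rule for a day without a text. Under the stated assumptions (24 sampled days resolved, 90% of taken doses texted, no false texts), the unstated coding choice moves the scored rate by about 20 points at true adherence of 80% and about 39 points at 50%. The movement shrinks if urine levels can be assigned to earlier days.

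What is affected is the AC adherence comparison, which is part of the primary objective in 2.1, secondary in 3.4 and exploratory in 6.2. The primary model in 6.3.2 is not affected. The net direction of bias relative to ROD cannot be determined from the documents. The change is worth making because the missing information can be collected only during the trial.

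**What to change.** - **Section 3.3:** add one row to the TLFB at each visit, in both arms, recording study medication as taken, partly taken or not taken for each day since the last visit.
- **Sections 3.4, 5.6 and 6.2:** name this row, the daily text and the urine levels as the sources for classifying AC days. State how they are combined when they disagree and how a level is assigned to days. A missing text alone should not set a day's status.
- **Section 6.2:** add a sensitivity analysis that codes untexted AC days as non-adherent, which matches how uncaptured ROD days are scored.

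The text stays as both the attention match and a prospective record, and the row supplements it.

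**Cost:** protocol wording and a minute or two in an interview already held at 24 visits. Recall over 3 to 4 days may overstate adherence. Asking both arms allows a same-method comparison, but it does not make the main contrast symmetric, because ROD days remain verified by video.

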### **3.2 Allocation to Interventional Group**

Participants will be randomized into one of two study groups based on proportion of use of prescription opiates and heroin, gender, and prior Suboxone® treatment.

### **3.3 Study Measures**

We will administer several standard assessments during the course of the study (shown below). At each office visit, subjects will complete standard questionnaires on mood, health behaviors, risky behaviors, and craving, and report all drug and alcohol use that has occurred since their last office visit:

Addiction Severity Index (McLellan et al. 1992). The ASI is a 45-minute interview which yields composite scores, ranging from 0 to 1, of problem severity over the past 30 days in 7 areas: medical, employment, drug use, alcohol use, legal, family/social, and psychiatric. Studies

CONFIDENTIAL

have shown moderate to excellent interrater and test-retest reliability. The ASI was used to characterize baseline demographic and drug use variables for each subject. The composite scores will be used as secondary outcome measures. The ASI will be administered at baseline week 5, week 9 and at the end of study.

Adverse events. Adverse events are queried and documented at each visit and recorded in the CRF.

Clinical Global Impression Scale (Guy 1976). The CGI is a brief clinical rating of severity of illness (at time of interview) and global improvement (from admission) using a 7-point Likert scale. The CGI is done by an observer and the subject to assess clinical progress, global improvement and to assess the severity of the subject's illness at regular contacts over the course of the study. The CGI is done once during baseline by the observer and participant, at week 9 and at the end of the study.

Columbia Suicide Severity Rating Scale (Chappell et al. 2012). This is a 5-item scale with additional questions that may be asked based on the participant's responses to the core items. This questionnaire will assess both lifetime and recent suicidal ideation and behavior, including both passive and active thoughts/plans. It is extensively used across clinical practices, hospitals, research institutions and schools to address potential thoughts of suicide expressed by the client. This questionnaire will be administered at baseline, and once a week through the trial. The CSSRS is a form that has been included in all pharmacotherapy trials as a safety measure.(U.S. Department of Health and Human Services n.d.) *Note: This data will not be analyzed but will be included to help ensure the safety of the participants.*

Concomitant medications will be queried and recorded at each participant visit.

Hamilton Depression Rating Scale (Hamilton 1967). The Ham-D is a 20-minute, 24-item interview that measures the severity of depression and changes in depressive symptoms. The Ham-D is administered at baseline, week 9 and at the end of the study.

Locator Form. The locator form asks about addresses and phone numbers where the participant might be contacted, as well as names and addresses of other individuals who might know the participant's whereabouts. The information is used to locate participants who do not respond to a calls and weekly text messages.

Obsessive Compulsive Drug Use Scale (Franken, Hendriks, and van den Brink 2002). Adapted from the Obsessive Compulsive Drinking Scale(Anton, Moak, and Latham 1995) (OCDS), measures craving for heroin on a 12-item likert scale. Our version replaces heroin with opioids more generally. This will be administered at baseline and weekly throughout the trial.

Risk Assessment Battery (Metzger et al. 1993). The RAB is a 38 item self-report questionnaire which assesses high risk behavior for exposure to the HIV virus. The RAB yields drug, sex and total risk scores and will be administered at baseline and at the end of the trial.

Systems Usability Scale (Grindrod, Li, and Gates 2014). The SUS is a 10 item self-reported validated measure of learnability and user satisfaction that we will use to evaluate the remote medication monitoring protocol. It uses a 5-point Likert scale to provide a quantitative measure of the usability of the ROD protocol and provides an overall score between 0 and 100. This scale will be administered at the end of the study.

Timeline Follow Back Interview (Sobell and Sobell 1995). The TLFB is a 15-30 minute, semi-structured interview adapted by our laboratory to collect information about daily drug, alcohol, and nicotine use. The TLFB will be given by trained research staff at baseline to cover 3 months immediately preceding treatment entry and will be updated at each research visit to determine any time spent in a controlled environment and cocaine, nicotine, and other drug use during the

CONFIDENTIAL

period since the last visit. The composite of these assessments are additive over the course of the study so that we will have continuous data.

Video Compliance. Submission of videos will be recorded (date and time) and assessed daily for compliance (i.e., taking the medication as prescribed). In addition, videos will be saved off the micro-SD cards at each office visit.

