### **5   Study Procedures**

See Measures for Description of Study Assessments

See Table 1 for Assessment Schedule

**Regular evaluation visits.** Subjects will have appointments with study staff two times weekly throughout the 12-week medication phase of the trial. A telephone reminder call and/or text message will be used to enhance attendance. Urine drug screens (UDS) for buprenorphine and norbuprenorphine will be obtained at each visit, along with concomitant medications, adverse events, and time line follow back (TLFB). The Columbia Suicide Severity Rating Scale (CSSRS) will be obtained at baseline and weekly. Other measures completed routinely but not weekly are listed in Table 1. A description and schedule of assessments is provided in the study measures section of the protocol. Each patient will meet weekly with the clinician who will assess clinical status, dispense study medications and monitor adverse events and concomitant medications.

After the completion of Week 13, or at the termination for patients who discontinue from the trial prematurely, we will conduct the following procedures: physical exam, electrocardiogram, monitor adverse events and concomitant medications, obtain blood samples for chemistry, CBC, obtain a urinalysis (and a pregnancy test for women), and complete other measures (See Table 1). The Systems Usability Scale will be conducted at the end of study visit. Safety follow up visit will be conducted one month after the completion of the medication phase.

**Psychosocial Treatment.** Subjects will participate in weekly Medication Management (MM), an intervention developed as part of NIAAA's Project COMBINE study, that provides advice and support from medical practitioners concomitantly with dispensing medications, safety checking and compliance (Pettinati et al., 2004). The main goal of MM is to increase the likelihood that patients will reduce their opioid use. The initial MM session is an hour; subsequent sessions are 15-30 minutes.

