### **5.2.2 Visits 2-4 (Suboxone Induction)**

Participants who are appropriate for the trial will be inducted onto Suboxone® using standard office based induction as described in the ASAM National Practice Guideline for the Use of Medications in the Treatment of Addiction Involving Opioid Use (Kampman, Kyle and Jarvis, Margaret 2015).

- Concomitant medications
- Medical Management, Pill Distribution
- Adverse Events
- Visit 4: Randomization & Distribution of Smartphone w/ intervention training

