### **5.2.3 Visits 5-28**

Patients will be seen twice weekly. For each in-office visit, patients will provide a urine sample that will be tested for drugs of abuse and for quantitative buprenorphine and norbuprenorphine levels. At each office visit, patients will also complete questionnaires about craving and depression. They will be asked about other medications they are using, about their drug and alcohol use since their last visit, and about any side effects they may be experiencing. Dosage adjustments will be made as needed at the discretion of their clinician. Subjects will also participate in weekly, manualized Medication Management. After induction, all patients will receive open-label Suboxone® for 12 weeks. Patients in both groups will receive a weeks' worth of Suboxone® at each medication management visit. After the 12 weeks of Suboxone®, subjects will be referred to on-going treatment options in the community.

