**Table 2: Study Schedule**

| Study Phase      | Study Week | Visit Number |
|------------------|------------|--------------|
| Baseline         | 1          | 1            |
| Induction Phase  | 2          | 2            |
|                  | 2          | 3            |
|                  | 2          | 4            |
|                  | 3          | 5            |
| Medication Phase | 3          | 6            |
|                  | 4          | 7            |
|                  | 4          | 8            |
|                  | 5          | 9            |
|                  | 5          | 10           |
|                  | 6          | 11           |
|                  | 6          | 12           |
|                  | 7          | 13           |
|                  | 7          | 14           |
|                  | 8          | 15           |
|                  | 8          | 16           |
|                  | 9          | 17           |
|                  | 9          | 18           |
|                  | 10         | 19           |
|                  | 10         | 20           |
|                  | 11         | 21           |
|                  | 11         | 22           |
|                  | 12         | 23           |
|                  | 12         | 24           |
|                  | 13         | 25           |
|                  | 13         | 26           |
|                  | 14         | 27           |
|                  | 14         | 28           |
| EOS              | 15         | 29           |

CONFIDENTIAL

This material is the property of the University of Pennsylvania.

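### The C-SSRS is kept as a weekly safety measure, but none is scheduled in induction week 2 or at the end-of-study/early termination visit; two short additions would close the gap

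*Combined protocol and SAP*

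**What the plan says.** - Section 3.3 (Study Measures), on the C-SSRS: "This questionnaire will be administered at baseline, and once a week through the trial". The same paragraph says that the data are collected for participant safety and will not be analysed.
- Section 5 (Study Procedures), under regular evaluation visits: "The Columbia Suicide Severity Rating Scale (CSSRS) will be obtained at baseline and weekly". That paragraph opens with twice-weekly appointments over the 12-week medication phase. For the end-of-study or termination visit, Section 5 names some procedures and refers to Table 1 for the rest.
- Table 1, C-SSRS row: 1X at baseline (V1), blank for week 2 (V2-V4), 12X for weeks 3-14 (V5-V28), blank at end of study (V29).
- Table 2 places V2-V4 in week 2 under "Induction Phase" and V29 in week 15.
- Section 5.2.2 lists for V2-V4 other medications, medical management with dispensing, and adverse events, and then "Visit 4: Randomization & Distribution of Smartphone w/ intervention training". It lists no C-SSRS.
- Sections 5.2.4 (end of study) and 5.5 (early termination) give the same list of procedures, without the C-SSRS.

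**The concern.** The C-SSRS is the plan's one dedicated screen for suicidal thoughts and behaviour. Two points of the trial have visits but no scheduled administration.

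The first is week 2, when participants start Suboxone. Section 3.3 speaks in general terms of mood questionnaires at office visits, but no mood scale is named for that week. Section 5.2.3 says "At each office visit, patients will also complete questionnaires about craving and depression", but that section covers visits 5-28.

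The second is exit from the trial. Section 5.4 allows withdrawal for not keeping to study procedures or the visit schedule and for worsening of opioid use disorder, and gives those who leave one final visit. A participant leaving for such reasons may have missed recent weekly assessments, and the final visit as listed does not make up for them.

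What is at stake is participant safety only: a missed chance to detect suicidality at treatment start or at exit.

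**Working it through.** The inputs are the C-SSRS row of Table 1 and the week numbering of Table 2 (weeks 1-15), with weeks taken as consecutive 7-day blocks.

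1. **Reproducing the 12X.** Weeks 3 to 14 inclusive: 14 − 3 + 1 = 12. One per week of the medication phase gives exactly the figure in Table 1.
2. **Weeks covered.** Week 1 plus weeks 3-14: 1 + 12 = 13 of 15. The two weeks with visits but no C-SSRS are week 2 (three visits) and week 15 (V29).
3. **Does other text fill the blanks?** For week 2, the list in 5.2.2 does not. For V29 and early termination, the lists in 5.2.4 and 5.5 do not. Those lists alone would not settle the matter, because Section 5 also points to Table 1 for further measures. The pointer leads to a blank C-SSRS cell, so it adds nothing.
4. **Interval across induction.** Week 1 is days 1-7 and week 3 is days 15-21. Nominal interval: 14 days. Shortest: 15 − 7 = 8. Longest: 21 − 1 = 20. For any two consecutive weeks the nominal interval is 7 days, the shortest 8 − 7 = 1 and the longest 14 − 1 = 13.
5. **Age of the last C-SSRS at a final visit.** After k fully missed weeks it is nominally 7 × (k + 1) days:
   - k = 0: 7 days. This also applies to a completer at V29, whose last C-SSRS is in week 14.
   - k = 1: 14 days.
   - k = 2: 21 days.
6. **With one added in week 2 and one at V29.** 1 + 1 + 12 + 1 = 15 of 15 weeks. The nominal gap across induction falls from 14 to 7 days, and a leaver who attends the final visit has a C-SSRS on that day.
7. **Added load.** 2 × 40 = 80 administrations, slightly fewer if some leavers attend no final visit.

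**The case against.** The strongest reply is that Table 1 is deliberate. The C-SSRS sentence in Section 5 stands in a paragraph about the 12-week medication phase, and weekly over 12 weeks is 12. Section 3.3 uses similar whole-trial wording for other measures that Table 1 also confines to weeks 3-14 apart from the baseline and end visits. The OCDUS is weekly and shares the 12X row; urine buprenorphine is twice weekly and appears as 24X (2 × 12), with week 2 blank. This reading is plausible. It is not conclusive, because Section 3 puts a urine screen at visit 4 that Table 1 leaves blank, so blanks in week 2 are not a fully reliable guide to intent. A reader might infer that the plan contradicts itself; the documents do not establish that.

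The second reply is that other monitoring covers the gap. Week 2 has three office visits, each with medical management and adverse-event questioning. Sections 5.9 and 7.2 require adverse events to be sought at every visit and contact. V1 includes both the C-SSRS and the HAM-D, and 4.3 excludes people whose psychiatric symptoms would, in the investigators' opinion, preclude participation. Table 1 schedules the HAM-D at V29 and, through Section 5's pointer, at termination. Completers have a week-14 C-SSRS, and regular attenders who leave have one about a week old. Section 5 also provides for a later contact: "Safety follow up visit will be conducted one month after the completion of the medication phase", although no C-SSRS is named for it. All of this stands. A reader might infer that suicidality goes unmonitored in week 2 or at exit, and that would overstate the case: what is missing is one dedicated instrument.

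Third, few people are affected at exit. At the 10% dropout assumed in 6.1, about 4 of 40 would leave (0.10 × 40), and only those who missed weeks and still attend a final visit would have a stale C-SSRS. The documents give no basis for estimating that subset. This also stands. The week-2 blank, by contrast, applies to every participant.

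**Conclusion.** The gap in the schedule is real. The C-SSRS is absent from Table 1 in week 2 and at V29, and no other text in the sections cited adds it there or at early termination. Because weekly within the medication phase is a fair reading, this is a minor, inexpensive safety improvement and not a demonstrated inconsistency.

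Its size is 2 of 15 study weeks without the scale, a nominal 14 days (8-20) between the first two administrations, and a last C-SSRS nominally 14 or 21 days old for someone who leaves after one or two missed weeks. These intervals rest on Table 2's week numbering and 7-day weeks. The text of 7.4.3 (Data and Safety Monitoring Plan) was not available for this check. It could not fill the cells of Table 1, but it may say something about suicidality that is not weighed here.

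A reader might also look for an effect on the trial's results. There is none: the scale is not analysed, so alpha, power and every efficacy comparison are untouched.

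**What to change.** Add one C-SSRS in week 2, for example at V4 before randomization, so that it is obtained in the same way whichever group the participant then joins. Add one at V29/early termination. Enter both in Table 1 and in the lists of 5.2.2, 5.2.4 and 5.5, so that staff working from either the table or the visit lists will give it.

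The cost is two short administrations per participant (about 80 for 40 participants) at visits that already take place, plus the text edits. No visit is added and no analysis needs revising.
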